### 10.3 Response Criteria and Methods for Evaluation of Measurable Disease

Diagnostic quality CT of the neck, chest, abdomen, and pelvis (N/C/A/P) will be performed at the end of Cycles 2, 7, 10, 13, and 16, and every 3 months after. PET-CT scans will be performed at end of Cycles 4, 10, and 16. Once PET-CT is negative, it does not need to be performed again. If CT/PET remains positive at the end of Cycle 4 and CT/PET scan to be performed at cycle 10 and 16, dedicated CT does not need to be performed at end of cycle 10 or 16. MRI may be performed at the Investigator's discretion for lesions not well-visualized by CT.

The determination of anti-tumor efficacy will be based on objective response assessments made according to the Revised Response Criteria for Malignant Lymphoma (Cheson et al. 2014) and treatment decisions by the investigator will be based on these assessments. Clinical response of progressive disease (PD), stable disease (SD), partial remission (PR), or complete remission (CR) will be determined at each assessment. Selection of up to 6 of the largest dominant nodes or nodal masses to follow for response assessment must be PET FDG-avid at baseline. Investigator evaluation of baseline radiographic assessment will enable study enrollment per Inclusion Criteria based on the presence of measurable disease > 1.5 cm evidenced by CT scan of the neck/neck/abdomen/pelvis or CT/PET scans. In addition, per the Revised Response Criteria for Malignant Lymphoma, these nodes or masses should be selected according to all of the following: they should be clearly measurable in at least 2 perpendicular dimensions; if possible, they should be from disparate regions of the body; and they should include mediastinal and retroperitoneal areas of disease whenever these sites are involved.

If the bone marrow was positive at baseline, a follow-up bone marrow aspirate and biopsy is required and must be negative for assessment of a CR. If the follow-up morphology is indeterminate, the biopsy tissue must be negative by immunohistochemistry or the patient will be assessed as a PR.

## 11.0 Statistical Considerations

---

### 11.1 Study Design

#### 11.1.1 Phase II

The primary hypothesis: in patients with relapsed/refractory Hodgkin Lymphoma (HL), the two agent regimen combination of ibrutinib and brentuximab vedotin (BV) can increase the complete response (CR) rate.

In a multi-center phase II trial investigating the use of single agent BV in relapsed/refractory HL patients post-AHCT, the overall response rate was 75%, the CR rate was 34%. Although single agent BV therapy is associated with a high overall response rate and tolerable toxicity, the CR rate and the duration of response can be improved.

This multi-center, single arm phase II trial will implement a Simon Two-Stage Minimax Design (Simon 1989; Jung 2004) to evaluate the antitumor activity of the two agent combination ibrutinib and brentuximab vedotin, as assessed by complete response (CR) rate, in patients with relapsed/refractory Hodgkin lymphoma. The study is expected to enroll a minimum of 19 and a maximum of 39 patients. The sample size is based on the desire to discriminate a promising CR rate of 50% from a disappointing response rate of 30% using a type I error rate of 0.05 and power of 80%.

At stage 1, 19 patients will be entered on the study. If  $\leq 6$  complete responses are seen, the study will be terminated. If at least 7 patients achieve a complete response, the trial will continue to the second stage.

At stage 2, 20 additional patients will be entered. At the end of stage 2, if 17 or more patients experience a complete response, the combination will be considered worthy of further study. If  $\leq 16$  patients experience a complete response then no further investigation of the combination is warranted.

#### 11.1.2 Safety Lead-In

Prior to formally initiating the phase II trial, a *patient safety lead-in* segment will be conducted to ensure there are no unexpected toxicities during cycle 1. Ultimately a total of 39 patients will be treated and evaluated for response at the ibrutinib/brentuximab vedotin doses considered safe -as determined during the *safety lead-in* segment of this study.

The first nine to twelve patients enrolled will be part of the *patient safety lead-in*. Initially, a group of up to 3 patients can be enrolled on dose level 1; given the potential for overlapping toxicity, the initial dose of ibrutinib tested will be 420 mg daily. During the *safety lead-in*, no more than 3 patients can be under active cycle 1 toxicity evaluation. . Note: Unacceptable toxicity in a given patient is defined as any non-hematologic grade 3|4 toxicity or, for hematologic toxicities, any grade 3|4 that does not resolve to a grade 1|2 within 7 days per NCI CTCAE v4.03 toxicity criteria and is considered at least possibly related to ibrutinib and/or brentuximab vedotin, or any other regimen-related cause of death.

The *safety lead-in* segment will follow standard 3+3 dose escalation/de-escalation/expansion rules based on observed toxicity during cycle 1: (Note: Dose de-escalation, escalation or cohort expansion will only take place after 3 patients are fully assessed using the Common Terminology Criteria for Adverse Events (CTCAE) of the National Cancer Institute (NCI) version 4.03 following the completion of cycle 1.)

- If 0 out of 3 evaluable patients experience unacceptable toxicity during cycle 1, then the next dose level of combination therapy will be tested.
- If 1 out of 3 evaluable patients experience unacceptable toxicity during cycle 1, three additional patients will be assessed at the same dose level of combination therapy.
- If 2 out of 3 evaluable patients experience unacceptable toxicity during cycle 1, dose escalation will cease and the next lower dose level of combination therapy will be expanded. Note: If 2 out of 3 experience unacceptable toxicity on dose level 1, the trial will be stopped. Doses below 420mg (ibrutinib)/1.8mg/kg (brentuximab vedotin) will not be considered.
- If 1 out of 6 evaluable patients experience unacceptable toxicity during cycle 1, then dose escalation to the next dose level of combination therapy will continue.
- If 2 or more out of 6 evaluable patients experience unacceptable toxicity during cycle 1, dose escalation will cease and the next lower dose level of combination therapy will be expanded. Note: If 2 or more out of 6 experience unacceptable toxicity on dose level 1, the trial will be stopped. Doses below 420 mg (ibrutinib)/1.8mg/kg (brentuximab vedotin) will not be considered.

The highest dose level that produces  $\leq 1/6$  evaluable patients with unacceptable toxicity during cycle 1 will be the declared safe dose and brought forward for phase II evaluation.

#### 11.2 Sample Size Accrual Rate

Assuming 1) the ibrutinib 560 mg and brentuximab vedotin 1.8mg/kg doses are well tolerated and 2) the study does not close for futility, 39 evaluable participants (received at least 1 cycle of treatment) will be enrolled on the phase II portion of the study. Study enrollment will be complete within 24 months from activation (accrual of 1-2 participants per month). Note: Expected accrual for the safety lead-in segment: n=9.

### 11.3 Safety Analysis and Stopping Rules for Excessive Toxicity

Following the *patient safety lead-in segment*, the early stopping rule for safety/toxicity will continue to be assessed for each patient after cycle 1. The expected rate of unacceptable toxicity should not be  $\geq 33\%$ . See section 5.1.7 for unacceptable toxicity definition. This rule is in addition to the quarterly review of all toxicities submitted to the COH DSMC. Given the number of patients treated, if the unacceptable toxicity rate is  $\geq 33\%$ , patient accrual will be halted and a full review of the data by the Data Safety Monitoring Committee (DSMC) will be mandated.

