### 10.1 Definitions

**Evaluable for toxicity:** All participants will be evaluable for toxicity from the time of their first treatment with ibrutinib plus brentuximab vedotin.

**Evaluable for objective response:** Only those participants who have measurable disease present at baseline, have received at least one cycle of therapy, and have had their disease re-evaluated will be considered evaluable for response. These participants will have their response classified according to the definitions stated below.

**Duration of overall response:** The duration of overall response is measured from the time measurement criteria are met for CR or PR, per Cheson criteria, (whichever is first recorded) until the first date that relapsed or progressive disease is objectively documented.

**Duration of overall CR:** The duration of overall CR is measured from the time measurement criteria are first met for CR until the first date that progressive disease is objectively documented.

**Duration of stable disease:** Stable disease is measured from the start of the treatment until the criteria for progression are met, per Cheson criteria, taking as reference the smallest measurements recorded since the treatment started, including the baseline measurements.

**Overall Survival (OS):** OS is defined as the duration of time from start of treatment to time of death (due to any cause).

**Progression-Free Survival (PFS):** PFS is defined as the duration of time from start of treatment to time of progression or death, whichever occurs first.

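### Does the 33% toxicity trigger in Section 11.3 need a stated denominator and first look before it can work alongside the lead-in rules?

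*Combined protocol and SAP*

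**What the plan says.** Section 11.3 is the whole of the rule. After the lead-in, "the early stopping rule for safety/toxicity will continue to be assessed for each patient after cycle 1". It continues: "Given the number of patients treated, if the unacceptable toxicity rate is" at or above 33%, "patient accrual will be halted and a full review of the data by the Data Safety Monitoring Committee (DSMC) will be mandated". For the definition of unacceptable toxicity it refers to Section 5.1.7, which uses the same definition as the lead-in. It gives no minimum number of patients.

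Section 10.1 adds: "All participants will be evaluable for toxicity from the time of their first treatment with ibrutinib plus brentuximab vedotin".

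Section 11.1.2 governs the lead-in, which has two ibrutinib dose levels:
- Decisions wait for a full cohort: "cohort expansion will only take place after 3 patients are fully assessed".
- On one event: "If 1 out of 3 evaluable patients experience unacceptable toxicity during cycle 1, three additional patients will be assessed at the same dose level".
- On two of three, or two or more of six: "dose escalation will cease and the next lower dose level of combination therapy will be expanded".
- The highest level with at most 1/6 "evaluable patients with unacceptable toxicity during cycle 1 will be the declared safe dose and brought forward for phase II evaluation".

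Section 11.2 expects nine lead-in patients and 39 evaluable phase II patients. Section 15.3 gives implementation of the stopping rules to the protocol management team, which includes the study biostatistician. Section 15.6 provides for quarterly reports to the DSMC and names a DSMC charter as a supplement, which is not among the documents reviewed.

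**The concern.** A rule applied after every patient's cycle 1 needs a numerator, a denominator and a starting point, and Section 11.3 leaves the last two open. Two possible readings sit awkwardly with the lead-in.

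- **All patients treated, both dose levels.** Suppose dose level 1 gives 0/3, level 2 gives 2/3, and the expansion of level 1 gives 1/3. Section 11.1.2 then clears level 1 at 1/6 and brings it forward. The same nine patients stand at 3/9, or 33.3%, which meets the trigger.
- **Phase II patients only, no minimum.** A single event among the first three patients (1/1, 1/2 or 1/3) halts accrual. In the lead-in, 1/3 leads to three more patients.

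At stake is an accrual pause caused by events at a dose already abandoned, or by one early event. In the other direction, a diluted count could be slow to react to a toxicity rate at the protocol's own limit.

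**Working it through.** **Inputs.** The trigger is a rate of at least 0.33, checked after each patient (Section 11.3). The lead-in rules are in Sections 5.1.7 and 11.1.2. Phase II has 39 patients (Section 11.1.1). The plan states no operating characteristics for the trigger, so there is no figure of its own to reproduce. The two-stage design that supplies the 39 does reproduce (exact type I error 0.0455, power 0.8036). The documents give no expected rate of unacceptable toxicity for the combination, so every true rate p below is an assumption.

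**1. Chance of a pause on the expected path.** This path is 0/3 at level 1 and at most 1/6 at level 2, with the same p at both. Let f_i(x) be the probability of x events, carried events included, after i phase II patients with no halt so far. Then

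f_i(x) = (1 − p)·f_{i−1}(x) + p·f_{i−1}(x − 1),

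and any probability with x/(i + n0) ≥ 0.33 is moved to the halted state. Here n0 is the number of lead-in patients carried (0, 6 or 9). Carried events are 0 or 1 with Bin(6, p) weights given at most one. At p = 0.20 the weights come from 0.8^6 = 0.262 and 6 × 0.2 × 0.8^5 = 0.393, that is 0.4 and 0.6.

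| Patients counted | p = 10% | p = 20% | p = 33% |
|---|---|---|---|
| Phase II only, from patient 1 | 30.0% | 59.8% | 90.5% |
| Six lead-in patients at the phase II dose carried | 1.8% | 15.3% | 63.9% |
| All nine lead-in patients carried | 0.1% | 4.0% | 42.5% |

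Most of the first row arises in the first three patients: 1 − (1 − p)^3 = 27.1%, 48.8% and 69.9%.

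**2. Effect of the first look, phase II patients only.** With a first look at 6, 10 or 19 patients, the chance of a pause is 44.4%, 27.3% or 14.4% at p = 20%, and 86.2%, 79.9% or 72.2% at p = 33%. Each delay reduces pauses at both rates.

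**3. The 3/9 case.** I enumerated the lead-in, treating 3/3 like 2/3 and requiring six patients to clear a level.

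- No path that clears level 2 reaches 33% pooled. The maximum is 2/12 = 16.7%.
- At 20% on both doses, level 1 is carried forward after a step-down with probability 0.226. Of those lead-ins, 27.1% stand at 33% or more pooled. Joint chance: 0.226 × 0.271 = 6.1%. For exactly 3/9: 0.226 × 0.176 = 4.0%.
- At 10% on both doses the joint chance is 1.3%.
- At 15% on level 1 and 40% on level 2 it is 0.595 × 0.405 = 24.1%.

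**4. Timing.** Section 11.3 starts after the lead-in and looks after each patient's cycle 1. If the first look follows the first phase II patient, 3/9 becomes 3/10 = 30% without a new event (no halt) or 4/10 = 40% with one. Likewise 4/12 becomes 4/13 = 30.8% without a new event. Only 4/9 and 5/12 then halt whatever that patient's outcome. At 20% on both doses their joint chance is 0.226 × (0.014 + 0.005) = 0.4%.

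**5. Counting only patients at the phase II dose, lead-in included.** The starting state is at worst 1/6. One new event gives 2/7 = 28.6% (no halt); two in a row give 3/8 = 37.5% (halt). A dose just cleared is therefore not halted on the data that cleared it, and one early event does not stop accrual.

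**The case for a change.** The strongest case for a change is that the same text supports rules that differ about fifteen-fold in pause probability at p = 20% (59.8% against 4.0%), and that this arises on the expected path, not only after a step-down. One reading pauses more often than not at a true 20%. Another misses more than half of trials at a true 33% (42.5% paused). The halt is automatic, the wording pulls both ways (the rule begins after the lead-in, yet is said to continue), and a sentence would settle it.

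The silence and the arithmetic stand. The inference that the plan must change is weaker.

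- The two extreme readings are the least natural. The phase II-only count fits poorly with a rule that continues from the lead-in. Pooling an abandoned dose is not required by Section 10.1, which says when a participant becomes evaluable for toxicity and does not define this denominator.
- The two rules do different jobs. Section 11.1.2 selects a dose; Section 11.3 calls for an independent look. A review when three of nine treated patients have had unacceptable toxicity does not contradict carrying the lower dose forward, and may be intended.
- No denominator or first look is better throughout. Steps 1 and 2 show that fewer pauses at 20% also mean fewer at 33%. A table of triggering counts could not be completed until that choice was made, because its largest denominator would be 39, 45, 48 or 51 depending on who is counted.

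**Conclusion.** The omission is real, but it is missing detail that the responsible team can fill sensibly. Counting patients at the phase II dose, lead-in patients included, fits the wording and avoids both conflicts. The 3/9 case needs pooled dose levels and a look at lead-in closure. On that reading, the chance of clearing level 1 after a step-down with the pooled rate at 33% or more is about 1% at an assumed 10% on both doses and 6% at 20%. It rises to 24% only in the scenario where the higher dose is far more toxic (15% and 40%), where a DSMC look is hardly out of place.

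The consequence is a reversible accrual pause with review. The trial is not terminated, no efficacy analysis is altered, and quarterly DSMC reporting runs regardless. What remains is a trade-off between sensitivity and false pauses, and that is the sponsor's to make. A clarifying sentence would do no harm, but the plan is workable without it. This conclusion rests on assumed toxicity rates and on a DSMC charter that was not available and may already settle the count.

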### 11.4 Statistical Analysis Plan

In general, data will be summarized by using counts and percents for discrete parameters, and by descriptive statistics (number of observations, mean, standard deviation, median, minimum and maximum) for continuous parameters. The complete response rate will be calculated as the percent of evaluable patients that have confirmed CR; exact 95% confidence intervals will be calculated for this estimate. Observed toxicities will be summarized in terms of type (organ affected or laboratory determination), severity, time of onset, duration, probable association with the study regimen and reversibility or outcome. Baseline information (e.g. the extent of prior therapy) and demographic information will be presented as well to describe the patients treated in this study. Time to response and survival endpoints will be estimated using the product-limit method of Kaplan and Meier. The cumulative incidence of relapse/progression and non-relapse mortality will be calculated as competing risks.

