#### **Statistical Considerations:**

The primary hypothesis is that, in patients with relapsed/refractory Hodgkin Lymphoma (HL), the two agent combination ibrutinib and brentuximab vedotin (BV) can increase the complete response (CR) rate.

In a multi-center phase II trial investigating the use of single agent BV in relapsed/refractory HL patients post-AHCT, the overall response rate was 75%, the CR rate was 34%. Although single agent BV therapy is associated with a high overall response rate and tolerable toxicity, the CR rate and the duration of response can be improved.

The primary objective is to evaluate the antitumor activity of the two agent combination ibrutinib and brentuximab vedotin, as assessed by complete response (CR) rate, in patients with relapsed/refractory HL. The primary endpoint is a confirmed tumor response of CR and is based on the Cheson Criteria. A single cycle of treatment will be given in a 21 day cycle. Each patient's disease status will be evaluated at baseline; response will be assessed as outlined in the study schema.

**Statistics/Sample Size and Accrual:** This study will implement a Simon Two-Stage (Minimax) Design to evaluate the activity of the two agent combination ibrutinib and brentuximab vedotin. The null hypothesis that the true CR rate is 30% will be tested against a one-sided alternative. The phase II portion of the study is expected to enroll a minimum of 19 and a maximum of 39 patients.

The sample size is based on the desire to discriminate a promising CR rate of 50% from a disappointing response rate of 30% using a type I error rate of 0.05 and power of 80%.

During the first stage, 19 patients will be entered on the study. If  $\leq 6$  complete responses are seen, the study will be terminated. If at least 7 patients achieve a complete response, the trial will continue to the second stage.

At the second stage, 20 additional patients will be entered. At the end of stage 2, if 17 or more patients experience a complete response, the combination will be considered worthy of further study. If  $\leq 16$  patients experience a complete response then no further investigation of the combination is warranted. A total of 39 patients will be included in the phase II portion of trial. The study will also have a lead in phase where a minimum of three patients will be enrolled with 420 mg oral daily dosing of ibrutinib.

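### Does the planned 95% interval for the CR rate need changing because at 17/39, where the trial just succeeds, it still contains the 30% null?

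*Combined protocol and SAP*

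**What the plan says.** The Synopsis (Statistical Considerations) sets the test: "The null hypothesis that the true CR rate is 30% will be tested against a one-sided alternative". Section 11.1.1 gives the design and its aim, to "discriminate a promising CR rate of 50% from a disappointing response rate of 30% using a type I error rate of 0.05" with 80% power. Nineteen patients enter stage 1. The trial stops at 6 or fewer CRs and otherwise adds 20 patients. At the end of stage 2, "if 17 or more patients experience a complete response, the combination will be considered worthy of further study"; at 16 or fewer it is not.

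Section 11.4 lists the summaries to be reported. For the CR rate among evaluable patients, "exact 95% confidence intervals will be calculated for this estimate". It does not name the exact method, say whether the interval is two-sided, or say whether it allows for the two-stage design. No section makes the interval a criterion for success or for stopping.

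**The concern.** The test spends its whole 5% in one tail. A two-sided 95% interval, the ordinary reading of 11.4, spends 2.5% in each. Any result with a one-sided p-value between 0.025 and 0.05 therefore rejects 30% by the test and keeps 30% in the interval. The success boundary falls in that band.

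A report of 17/39 would then call the combination worthy of further study beside an interval that includes the rate the protocol calls disappointing. The plan has no 90% interval, one-sided bound or design-based p-value to put next to it, and one added after the result could look selected. What is at stake is how the report reads, not the decision.

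**Working it through.** **Inputs.** Null 30%, one-sided (Synopsis). Target 50%, type I error 0.05, power 80%, n1 = 19, stop at 6 or fewer, n2 = 20, success at 17 or more (Section 11.1.1). Exact 95% interval (Section 11.4), read as two-sided. Denominator taken as 39 evaluable patients (Section 11.2).

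**1. The design.** With X1 ~ Bin(19, p) and X2 ~ Bin(20, p),

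P(success | p) = sum over k = 7 to 19 of P(X1 = k) × P(X2 ≥ 17 − k).

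- p = 0.30: 0.0455, within the 0.05 limit.
- p = 0.50: 0.8036, above 80%.
- A search over all two-stage designs finds none with fewer than 39 patients that meets both limits. Among those with 39, this one has the smallest expected size under the null (25.7).

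The plan's figures reproduce.

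**2. The interval at the boundary.** The ordinary exact (Clopper-Pearson) 95% limits for x of n are the 2.5% quantile of Beta(x, n − x + 1) and the 97.5% quantile of Beta(x + 1, n − x). The two-stage exact limits replace the binomial tails with those of the two-stage design, placing stage-1 stops below all stage-2 outcomes and ordering the latter by total CRs.

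| CRs of 39 | Rule | Two-stage p at 30% | Ordinary 95% | Two-stage 95% | Two-stage 90% |
|---|---|---|---|---|---|
| 16 | fail | 0.0810 | 25.6–57.9% | 26.1–59.4% | 28.2–56.7% |
| 17 | success | 0.0455 | 27.8–60.4% | 28.1–61.1% | 30.3–58.6% |
| 18 | success | 0.0230 | 30.1–62.8% | 30.3–63.2% | 32.5–60.7% |

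Both 95% intervals contain 30% at 17/39, so the cause is the confidence level and not the choice of exact method. Over stage-2 counts 7 to 39, the ordinary lower limit disagrees with the rule only at 17. An ordinary 90% interval at 17/39 starts at 30.001%, which would print as 30.0%.

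**3. How often.** P(exactly 17) and its share of successes:

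- true rate 30%: 0.0225 / 0.0455, about 50% of false successes;
- true rate 40%: 0.1010 / 0.3558, about 28%;
- true rate 50%: 0.0812 / 0.8036, about 10%.

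**4. What the matched interval would do elsewhere.** The two-stage 90% interval agrees with the rule at every count in one sense: its lower limit exceeds 30% exactly when the rule says success. Its upper limit behaves differently at low stage-2 counts, because the ordering ranks every stage-1 stop below them.

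| CRs of 39 | Raw rate | Ordinary 95% | Two-stage 90% |
|---|---|---|---|
| 7 | 17.9% | 7.5–33.5% | 18.8–53.0% |
| 12 | 30.8% | 17.0–47.6% | 21.5–53.1% |

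At each count from 7 to 12 its upper limit is about 53%, so a clear failure would carry an interval that includes the 50% target; the ordinary 95% interval excludes 50% at all six counts. At 7/39 it also excludes the observed rate, though that outcome is very rare (about 0.01% at a true rate of 30%). Counts 7 to 12 have probability 9.3% at a true rate of 30%, against 2.3% for exactly 17. At 40% the order reverses: 3.4% against 10.1%.

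**5. Denominator.** Section 10.1 requires disease re-evaluation before a patient counts as evaluable for response; Section 11.2 requires only one cycle. If the denominator falls below 39, the ordinary 95% lower limit at 17 CRs is 28.6% for 38, 29.5% for 37 and 30.4% for 36. With 36 the overlap at 17 is gone.

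**The case for a change.** The best case for a change is that it is cheap and falls on the count that matters most. Seventeen is the success boundary, it makes up about half of all false successes, and one sentence in 11.4 would fix in advance which interval stands beside the decision. Section 11.4 neither labels its interval descriptive nor names the method, and reading it as a one-sided bound would exclude 30% only by 0.001 percentage points.

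The arithmetic in this stands, and so does the remark that 11.4 is terse. The inference does not. A one-sided 5% test and a two-sided 95% interval are different statements at different levels, so an interval that contains 30% does not contradict a test that rejects it. No later choice of interval is needed, because one is already planned and the count has already decided. The half-of-false-successes figure is the same 2.3% expressed as a share. Nor would the matched interval end the mixed messages: it removes one at 17/39 and brings in others at 7 to 12 CRs.

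**Conclusion.** The mismatch is real but confined to one outcome, and it is a matter of reporting. The pre-specified CR count decides, and following the plan as written gives a sound result with the stated error rates. The coverage of the planned interval is not in question either: under the two-stage design the ordinary 95% interval covers at least 94.6% over true rates from 10% to 80%. An analyst can report 17/39 with its 95% interval and say that the one-sided count rule was met at p = 0.0455. Replacing or supplementing the interval is a trade-off between readings at different counts, with no clear gain.

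This rests on reading 11.4 as a two-sided 95% interval and on 39 evaluable patients.

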**Secondary Objectives:**

- Assess the safety and tolerability of the two agent combination through evaluation of toxicities, including type, frequency, severity, attribution, time course and duration.
- Obtain estimates of overall response rate (ORR), response duration and survival (overall and progression-free).
- Describe outcomes of patients who ultimately undergo autologous or allogeneic hematopoietic cell transplantation following treatment with ibrutinib/brentuximab vedotin.

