### 10.2 Transplant Endpoint Definitions

**Overall Survival (OS):** OS is defined as the duration of time from start of HCT treatment to time of death (due to any cause). Evaluated and recorded at day 30, day 100, 6 months, 1-year and 2-years post HCT.

**Progression-Free Survival (PFS):** PFS is defined as the duration of time from start of HCT treatment to time of progression or death, whichever occurs first. Evaluated and recorded at day 30, day 100, 6 months, 1-year and 2-years post HCT.

**Relapse/Progression (CIR):** The event is relapse/progression. The time to this event is measured from start of HCT treatment. Deaths without relapse/progression are considered a competing risk. Surviving patients with no history of relapse/progression are censored at time of last follow-up. Evaluated and recorded at day 30, day 100, 6 months, 1-year and 2-years post HCT.

**Non-relapse mortality (NRM):** NRM is defined as death occurring in a patient from causes other than relapse or progression. NRM is measured from start of treatment until non-disease related death, or last follow-up, whichever comes first. Deaths from relapse/progression are considered a competing risk. Evaluated and recorded at day 30, day 100, 6 months, 1-year and 2-years post HCT.

**Stem cell mobilization:** mobilization regimen used, median number of cells collected, median number of days to reach minimum collection.

**Engraftment (Recovery of Granulopoiesis and Megakaryopoiesis):** Engraftment will be assessed using three distinct milestones: 1) (Autologous and Allogeneic) ANC (neutrophils)  $\geq 0.5 \times 10^3/\mu\text{L}$  achieved and sustained for 3 consecutive lab values on different days with no subsequent decline; 2) (Autologous) Platelets (PLT)  $\geq 20 \text{ K}/\mu\text{L}$  independent of platelet transfusion support; and 3) (Allogeneic) PLT  $\geq 25 \text{ K}/\mu\text{L}$

independent of platelet transfusion support. For platelet recovery, date should reflect no transfusions in previous 3 days and the first of 3 consecutive lab values on different days.

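### Section 11.4 assigns Kaplan-Meier to an undefined time to response; if patients who progress, die or start new treatment before responding are censored, the curve overstates the probability of response

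*Combined protocol and SAP*

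**What the plan says.** Section 11.4 (Statistical Analysis Plan) gives the method in one sentence: "Time to response and survival endpoints will be estimated using the product-limit method of Kaplan and Meier". The sentence after it reads: "The cumulative incidence of relapse/progression and non-relapse mortality will be calculated as competing risks". Response is not among the endpoints given competing-risk treatment.

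Section 10.2 shows that the plan knows the principle. For post-transplant relapse it says: "Deaths without relapse/progression are considered a competing risk".

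Section 10.1 defines duration of response, duration of CR, duration of stable disease, overall survival (OS) and progression-free survival (PFS). It does not define time to response. No start point is given, no event (CR, or CR/PR), no population, and no rule for patients who never respond. Section 1.0 lists overall response rate, response duration, OS and PFS as secondary estimates; time to response is not listed.

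The response rate is handled separately in 11.4: "The complete response rate will be calculated as the percent of evaluable patients that have confirmed CR", with an exact 95% interval.

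The synopsis (Estimated Duration of the Study) says that patients who stop treatment without relapse or progression go on being assessed until relapse or progression, new anticancer treatment, or death.

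**The concern.** Kaplan-Meier treats a censored patient as someone who could still have the event and is represented by those still at risk. That does not fit a patient whose disease has progressed, who has died, or who has moved to other anticancer treatment before responding. For time to CR, transplant in partial response is a further route out, which Sections 2.4.1 and 5.2 allow. Each of these ends the chance of a response to the study regimen, just as death without relapse ends the chance of relapse in 10.2.

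If such patients are censored, their share of the risk set is passed to those who remain, and the curve rises above the proportion who actually respond. The report would then carry a response proportion and, beside it, a time-to-response curve ending higher. In a single-arm trial read against historical rates (34% CR and 75% overall response in Section 11.1.1), a reader could take the end of the curve as a response probability. A median time to response read from it would also come too early.

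**Working it through.** The documents give no figure for time to response, so there is none to reproduce. The check compares the two estimators under stated assumptions.

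**Inputs from the documents**
- True CR rate p = 0.50, the target rate in Section 11.1.1.
- 21-day cycles, with PET-CT at the end of cycles 4, 10 and 16 (Section 10.3): weeks 12, 30 and 48.
- Maximum phase II size of 39.

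**Assumptions (not in the documents)**
- Share of CRs first seen at those scans: either 70/20/10%, or all after cycle 4.
- Non-responders leave by progression, death or new treatment, exponentially with median m = 40, 20 or 10 weeks, and are censored then.

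**Formulas**
- Events at scan k: d_k = p × f_k, where f_k is the share of CRs seen at that scan.
- At risk: n_k = (responders not yet in CR) + (1 − p) × 2^(−t_k/m).
- Curve: 1 − KM = 1 − Π(1 − d_k/n_k).
- With competing events, cumulative incidence is Σ d_k, which ends at p = 0.50 whatever m is.

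**CRs at cycles 4/10/16 in the ratio 70/20/10, m = 40 weeks**
- Week 12: n = 0.50 + 0.4061 = 0.9061, d = 0.35, factor 0.6137.
- Week 30: n = 0.15 + 0.2973 = 0.4473, d = 0.10, factor 0.7764.
- Week 48: n = 0.05 + 0.2176 = 0.2676, d = 0.05, factor 0.8132.
- 1 − KM = 1 − 0.6137 × 0.7764 × 0.8132 = 0.61.

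The same steps for each median:

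| Median exit | Week 12 (true 35%) | Week 30 (true 45%) | Week 48 (true 50%) | Expected at risk of 39 at week 48 |
|---|---|---|---|---|
| 40 weeks | 39% | 52% | 61% | 10.4 |
| 20 weeks | 42% | 60% | 74% | 5.6 |
| 10 weeks | 49% | 73% | 93% | 2.6 |

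In all three rows the curve passes 50% by week 30, whereas cumulative incidence reaches 50% only at week 48.

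**All CRs after cycle 4**
- m = 40: 0.50/0.9061 = 0.55.
- m = 20: 0.50/0.8299 = 0.60.
- m = 10: 0.50/0.7176 = 0.70.

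**Second timing pattern, on the six assessments in Section 2.2 (cycles 2, 4, 7, 10, 13, 16)**

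Non-responders leave just after these assessments in shares of 25/25/20/15/10/5%.
- Responses early (50/40/10% at the first three): at risk 1.000, 0.625, 0.300; events 0.25, 0.20, 0.05. 1 − KM = 1 − 0.75 × 0.68 × 0.8333 = 0.575.
- Responses spread (40/30/15/8/4/3%): at risk 1.000, 0.675, 0.400, 0.225, 0.110, 0.040; events 0.20, 0.15, 0.075, 0.04, 0.02, 0.015. 1 − KM = 0.79, with 39 × 0.040 = 1.6 patients expected at risk at the last scan.

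**No excess**
- If non-responders stay in the risk set to the last assessment, the product telescopes and 1 − KM = 0.50 exactly.
- In a responders-only analysis nobody is censored, so the bias cannot arise.

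**Primary analysis**

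The two-stage design (continue with at least 7 CRs in 19, succeed with at least 17 in 39) has exact one-sided type I error 0.0455 at 30% and power 0.8036 at 50%. Both come from binomial counts; the curve does not enter.

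**The case against.** The strongest reply is that 11.4 names only an estimator. No section says that patients who progress, die or change treatment are censored for time to response. Analysing responders only, or holding non-responders at risk to the last scan, fits the same sentence and gives no bias. This stands, and it is why the point is conditional. It does not remove the need for an edit, because the plan leaves the choice open and its plainest reading, all patients with non-responders censored at last assessment, is the biased one.

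The sentence may also be loose wording for response duration, a listed objective for which 11.4 names no other method and Kaplan-Meier is conventional. That is possible and cannot be settled from the text. If so, the sentence still needs correcting.

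The largest excesses are fragile. With a 10-week median, 1 − 2^(−1.2) = 56% of non-responders have gone by week 12, although Section 5.2 expects at least four cycles unless there is progression or intolerable toxicity. Section 10.1 requires one cycle and a re-evaluation before a patient counts as evaluable for response, so some very early exits may not be in the analysis. Much of the excess also builds up at the last scan, where few remain at risk. These points stand, and the 93% should not be used as a headline.

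A reader might infer that anyone who leaves treatment is lost to the response analysis. The synopsis does not support that: assessment continues after treatment stops without progression. Only progression, death and new anticancer treatment matter here.

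**Conclusion.** The point holds in conditional form. Section 11.4 assigns Kaplan-Meier to an endpoint that is not defined, and withholds from it the competing-risk treatment given to relapse and non-relapse mortality in the next sentence. If patients who progress, die or start new anticancer treatment (including transplant, for time to CR) are censored before responding, the curve overstates the probability of response.

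For a true CR rate of 50% and median exits of 40 or 20 weeks, the excess is about 5 to 10 points if all CRs come after cycle 4, and 11 to 24 points if they come after cycles 4, 10 and 16 in the ratio 70/20/10. Larger values need very early exits and rest on few patients at risk. The excess is zero if non-responders remain at risk or only responders are analysed. Response and exit timing are assumptions throughout.

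Two stronger readings go beyond the documents. One is that the planned curve will certainly rise well above the response rate; the censoring rule that this requires is not written. The other is that the curve contradicts the reported CR rate; that rate is a separate proportion with its own exact interval, and no response rate is planned from the end of the curve. The CR rate, the two-stage rule and the sample size are unaffected, and time to response is not a stated objective. This is a minor improvement.

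**What to change.** In 11.4, replace the time-to-response part of the sentence with one of two options:
- Cumulative incidence of response from start of treatment, stating whether the event is CR or CR/PR and which patients are included, with progression, death and new anticancer treatment before response as competing events. For time to CR, say that transplant counts as new anticancer treatment.
- Median and range of time to response among responders only, labelled as such.

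Keep Kaplan-Meier for OS, PFS and duration of response, and name duration of response explicitly, since it is an objective and 11.4 does not mention it. A one-line definition in 10.1 would complete the change.

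The cost is one or two sentences. No new data are needed: dates of response, progression, death and further anticancer treatment are already to be collected. The design, sample size and primary analysis do not change.
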